12 SAFETY, MONITORING AND QUALITY ASSURANCE

12.1 Adverse Event Collection and Reporting Information:

- Adverse Event (AE): any new untoward medical occurrence or worsening of a preexisting medical condition in a clinical investigation participant administered study drug and that does not necessarily have a causal relationship with this treatment. An AE can therefore be any unfavorable and unintended sign (such as an abnormal laboratory finding), symptom, or disease temporally

associated with the use of investigational product, whether or not considered related to the investigational product

- Non-serious adverse event: an AE not classified as serious
- Serious Adverse Event (SAE): any untoward medical occurrence that at any dose:
 - results in death
 - is life-threatening (defined as an event in which the participant was at risk of death at the time of the event; it does not refer to an event which hypothetically might have caused death if it were more severe)

- [REDACTED]
- results in persistent or significant disability/incapacity
- is a congenital anomaly/birth defect
- [REDACTED]

or at home for allergic bronchospasm; blood dyscrasias or convulsions that do not result in hospitalization.)

-
-

(unless considered an important medical or life-threatening event)

- The causal relationship to study drug is determined by a physician and should be used to assess all adverse events (AE). The causal relationship can be one of the following:
 - Related: There is a reasonable causal relationship between study drug administration and the AE.
 - Not related: There is not a reasonable causal relationship between study drug administration and the AE.
 - The term "reasonable causal relationship" means there is evidence to suggest a causal relationship.
- An appropriate SAE form (Medwatch form) should be used to report SAEs to BMS. If the Sponsor-Investigator prefers to a study specific/Institutional form, it must be sent to the BMS ISR Trial Manager prior to study initiation for internal BMS review to ensure that at a minimum all of the data elements on the CIOMS form are present.

12.2 Serious Adverse Event Collection and Reporting

- All Serious Adverse Events (SAEs) that occur following the subject's written consent to participate in the study through 30 days of discontinuation of dosing must be reported to BMS Worldwide Safety, whether related or not related to study drug.
- Following the subject's written consent to participate in the study, all SAEs, whether related or not related to study drug, are collected, including those thought to be associated with protocol-specified procedures. The Investigator should report any SAE occurring after these aforementioned time periods, which is believed to be related to study drug or protocol-specified procedure.
- An SAE report should be completed for any event where doubt exists regarding its seriousness.

- If the Investigator believes that an SAE is not related to study drug but is potentially related to the conditions of the study (such as withdrawal of previous therapy or a complication of a study procedure), the relationship should be specified in the narrative section of the SAE Report Form.
- SAEs, whether related or not related to study drug, and pregnancies must be reported to BMS within 24 hours \ 1 Business Day of becoming aware of the event. SAEs must be recorded on either CIOMS, MedWatch, or approved study specific/institutional SAE form.
 - SAE Email Address: [contact]
 - SAE [contact]
- If only limited information is initially available, follow-up reports are required
- If an ongoing SAE changes in its intensity or relationship to study drug or if new information becomes available, a follow-up SAE report should be sent within 24 hours \ 1 Business Day to BMS using the same procedure used for transmitting the initial SAE report.
- All SAEs should be followed to resolution or stabilization.

12.3 Expedited and periodic safety update reporting by BMS

- It is the Sponsor-Investigator's responsibility to report events to their Local HA. In addition, suspected serious adverse reactions (whether expected or unexpected) shall be reported by BMS to the relevant competent health authorities in all concerned countries according to local regulations (either as expedited and/or in aggregate reports).
- In accordance with local regulations, BMS will notify Sponsor-Investigator of all reported SAEs that are suspected (related to the investigational product) and unexpected (ie, not previously described in the IB). An event meeting these criteria is termed a Suspected, Unexpected Serious Adverse Reaction (SUSAR). Sponsor-Investigator notification of these events will be in the form of either a SUSAR Report or a Semi-Annual SUSAR Report. Sponsor-Investigator (or delegate) will receive these reports through the FastTrack portal.
- Other important findings which may be reported by BMS as an Expedited Safety Report (ESR) include: increased frequency of a clinically significant expected SAE, an SAE considered associated with study procedures that could modify the conduct of the study, lack of efficacy that poses significant hazard to study subjects, clinically significant safety finding from a nonclinical (eg, animal) study, important safety recommendations from a study data monitoring committee, or Sponsor-Investigator or BMS decision to end or temporarily halt a clinical study for safety reasons.
- Upon receiving an ESR from BMS, the Sponsor-Investigator must review and retain the ESR with the IB. Where required by local regulations or when there is a central IRB/IEC for the study, the Sponsor-Investigator will submit the ESR to the appropriate IRB/IEC. The investigator and IRB/IEC will determine if the informed consent requires revision. The investigator should also comply with the IRB/IEC procedures for reporting any other safety information.

12.4 Non-Serious Adverse Event Collection and Reporting

- The collection of non-serious AE information should begin following the subject's written consent to participate in the study. All non-serious adverse events (not only those deemed to be treatment-related) should be collected continuously during the treatment period and for a minimum of 400 days following the last dose of study treatment.
- Non-serious AEs should be followed to resolution or stabilization or reported as SAEs if they become serious. Follow-up is also required for non-serious AEs that cause interruption or discontinuation of study drug and for those present at the end of study treatment as appropriate.

- Non-serious Adverse Events (AE) are to be provided to BMS in aggregate via interim or final study reports as specified in the agreement or, if a regulatory requirement [eg, IND US trial] as part of an annual reporting requirement.

12.5 Pregnancy:

- If, following initiation of the investigational product, it is subsequently discovered that a study participant is pregnant or may have been pregnant at the time of investigational product exposure, including during at least 5 half-lives after product administration, the investigational product will be permanently discontinued in an appropriate manner.
- The Sponsor-Investigator must immediately notify [contact] of this event and complete one of the following forms within 24 hours of awareness of the event via either the CIOMS, MedWatch or appropriate Pregnancy Surveillance Form in accordance with SAE reporting procedures.
- Protocol-required procedures for study discontinuation and follow-up must be performed on the participant.
- Follow-up information regarding the course of the pregnancy, including perinatal and neonatal outcome and, where applicable, offspring information must be reported on the CIOMS, MedWatch, BMS Pregnancy Surveillance Form, or approved site SAE form. A BMS Pregnancy Surveillance Form may be provided upon request.
- Any pregnancy that occurs in a female partner of a male study participant should be reported to BMS. Information on this pregnancy will be collected on the Pregnancy Surveillance Form. In order for Sponsor-Investigator or designee to collect any pregnancy surveillance information from the female partner, the female partner must sign an informed consent form for disclosure of this information.

12.6 Laboratory Test Abnormalities

- All laboratory test results captured as part of the study should be recorded following institutional procedures. Test results that constitute SAEs should be documented and reported to BMS as such.
- The following laboratory abnormalities should be documented and reported appropriately:
 - any laboratory test result that is clinically significant or meets the definition of an SAE
 - any laboratory abnormality that required the participant to have study drug discontinued or interrupted
 - any laboratory abnormality that required the subject to receive specific corrective therapy.
 - It is expected that wherever possible, the clinical rather than laboratory term would be used by the reporting investigator (e.g., anemia versus low hemoglobin value).

12.7 Other Safety Considerations:

- Any significant worsening noted during interim or final physical examinations, and any other potential safety assessments, whether or not these procedures are required by the protocol, should also be recorded as a non-serious or serious AE, as appropriate, and reported accordingly.

12.8 Adverse Event Reconciliation Process

- The Sponsor-Investigator (or designee) will reconcile the clinical database AE cases (case level only) transmitted to BMS Global Pharmacovigilance ([contact]).

- The Sponsor-Investigator will request the SAE reconciliation report (and include the BMS protocol number) from BMS GPV&E ([contact]) every 3 months and prior to data base lock or final data summary
- GPV&E will send the Sponsor-Investigator the report to verify and confirm all AE and SAEs have been transmitted to BMS GPV&E.
- The data elements listed on the GPV&E reconciliation report will be used for case identification purposes. If the Sponsor-Investigator determines a case was not transmitted to BMS GPV&E, the case should be sent immediately to BMS ([contact]).

12.9 Product Quality Complaints (PQCs)

- Definitions:
 - Any communication about a BMS Product that alleges deficiencies related to identity, quality, durability, reliability, safety, effectiveness, performance, tampering, diversion, and/or counterfeiting/falsification of a drug, combination product, or device after it is released for distribution to market or clinic by either: (1) BMS or (2) distributors or partners for whom BMS manufactures the material. This includes all components co-packaged with the drug, such as drug containers, delivery system, labelling, and inserts.
 - BMS product: Commercial or investigational materials (i.e., drugs, devices, biologics or any combination thereof) and their packaging components, whether they are produced or distributed by BMS or by third parties under contract with BMS, and products that are being manufactured for BMS by third parties.
- Reporting:
 - Product Quality Complaints must be reported to BMS within one (1) business day of awareness to [contact].
 - In the event of a suspected product quality issue, the affected product must be quarantined immediately at the Investigational site.
 - The affected product should not be disposed unless retention presents a risk to personnel (e.g., cytotoxic, risk of injury from broken glass or sharps).
 - When reporting, as much product information as possible should be reported. At a minimum, but not limited to, include:
 - ISR Study number, site reference, product description, impacted batch number, container number(s), photographs, and any other supporting information

12.10 Data Safety Monitoring Plan

All data will be collected in a timely manner and reviewed by the principal investigator or co-investigator. Adverse events will be reported as required above. Any safety concerns, new information that might affect either the ethical and or scientific conduct of the trial, or protocol deviations and violations will be immediately reported to the IRB, and if applicable to the Sponsor.

13 PRIVACY AND CONFIDENTIALITY

- Study procedures will be conducted in a private setting
- Only data and/or specimens necessary for the conduct of the study will be collected

Mass General Brigham Institutional Review Board
Intervention/Interaction Detailed Protocol

- Data collected (paper and/or electronic) will be maintained in a secure location with appropriate protections such as password protection, encryption, physical security measures (locked files/areas)
- Specimens collected will be maintained in a secure location with appropriate protections (e.g. locked storage spaces, laboratory areas)
- Data and specimens will only be shared with individuals who are members of the IRB-approved research team or approved for sharing as described in this IRB protocol
- Data and/or specimens requiring transportation from one location or electronic space to another will be transported only in a secure manner (e.g. encrypted files, password protection, using chain-of-custody procedures, etc.)
- All electronic communication with participants will comply with Mass General Brigham secure communication policies
- Identifiers will be coded or removed as soon as feasible and access to files linking identifiers with coded data or specimens will be limited to the minimal necessary members of the research team required to conduct the research
- All staff are trained on and will follow the Mass General Brigham policies and procedures for maintaining appropriate confidentiality of research data and specimens
- The PI will ensure that all staff implement and follow any Research Information Service Office (RISO) requirements for this research
- Additional privacy and/or confidentiality protections:
N/A

15 APPENDICES

15.1 Appendix A – Study Scheme

15.2 Appendix B – Study Assessments & Procedures

Visit	1 Screening	2 Baseline	3 Week 4	4 Week 8	5 Week 12	6 Week 16	7 Week 20	8 (EOS) Week 24	Early Termination
Informed consent	X								
Inclusion/exclusion criteria	X								
Medical history	X								
Prior/concurrent medications	X	X	X	X	X	X	X	X	X
New symptoms/side effects		X	X	X	X	X	X	X	X
Dispense study medication		X	X	X	X	X	X		
Assess medication compliance			X	X	X	X	X	X	X
Assessments									
Vital signs		X				X		X	X
Physical exam		X				X		X	X
ppPASI		X	X	X	X	X	X	X	X
PGA		X	X	X	X	X	X	X	X
DLQI		X	X	X	X	X	X	X	X
EQ-5D-5L		X	X	X	X	X	X	X	X
VAS-itch		X	X	X	X	X	X	X	X
VAS-pain		X	X	X	X	X	X	X	X
Photographs (Optional)		X	X	X	X	X	X	X	X
Laboratory Studies									
Urine pregnancy test	X								
CBC, CMP	X					X		X	X
HIV Test	X								
CPK	X					X		X	X
Triglycerides	X					X		X	X
Hep C antibody	X								
Hep B surface antigen	X								
QuantiFERON GOLD TB screen	X								

15.3 Appendix C – Palmoplantar Pustulosis – Psoriasis Area and Severity Index (ppPASI)

Disease severity (erythema (E), pustules/vesicles (P), desquamation/scales (D) and area involved) is assessed separately on the right palm, left palm, right sole and left sole.

Score	Erythema (E)	Pustules (P)	Desquamation (D)	Area Involved (%)
0	None	None	None	0
1	Slight	Slight	Slight	0 – 10
2	Moderate	Moderate	Moderate	11 – 30
3	Severe	Severe	Severe	31 – 50
4	Very Severe	Very Severe	Very Severe	51 – 70
5				70 – 90
6				91 - 100

Calculation of the Palmoplantar Pustulosis – Psoriasis Area and Severity Index (ppPASI):

ppPASI Score = [(right palm: E+P+D)*right palm_area*0.2] + [(left palm: E+P+D)*left palm_area*0.2] + [(right sole: E+P+D)*right sole_area*0.3] + [(left sole: E + P + D) *left sole_area * 0.3]

15.4 Appendix D – Physician’s Global Assessment

Please score the patient’s skin as a global assessment (palms and soles) on the disease present on your examination today.

Score	Category	Description
0	Clear	No visible signs of palmoplantar psoriasis
1	Almost Clear	Just perceptible erythema, scaling and/or rare pustules
2	Mild	Light pink erythema with few pustules
3	Moderate	Pustules on a red erythematous base with or without, thickening of the skin
4	Severe	Pustules, coalescing into lakes, dark red to violaceous plaques with scaling and thickening of the skin

15.5 Appendix E – Dermatology Life Quality Index

Patient ID:

Date:

The aim of this questionnaire is to measure how much your skin problem has affected your life OVER THE LAST WEEK. Please check one box for each question.

1.	Over the last week, how itchy, sore, painful or stinging has your skin been?	Very much A lot A little Not at all	   	
2.	Over the last week, how embarrassed or self conscious have you been because of your skin?	Very much A lot A little Not at all	   	
3.	Over the last week, how much has your skin interfered with you going shopping or looking after your home or yard ?	Very much A lot A little Not at all	   	Not relevant 
4.	Over the last week, how much has your skin influenced the clothes you wear?	Very much A lot A little Not at all	   	Not relevant 
5.	Over the last week, how much has your skin affected any social or leisure activities?	Very much A lot A little Not at all	   	Not relevant 
6.	Over the last week, how much has your skin made it difficult for you to do any sport ?	Very much A lot A little Not at all	   	Not relevant 
7.	Over the last week, has your skin prevented you from working or studying ?	yes no	 	Not relevant 
	If "No", over the last week how much has your skin been a problem at work or studying ?	A lot A little Not at all	  	
8.	Over the last week, how much has your skin created problems with your partner or any of your close friends or relatives ?	Very much A lot A little Not at all	   	Not relevant 

Mass General Brigham Institutional Review Board
Intervention/Interaction Detailed Protocol

9.	Over the last week, how much has your sexual difficulties skin caused any	Very much 	A lot 	A little 	Not at all 	Not relevant 
10.	Over the last week, how much of a problem has the treatment for your skin been, for example by making your home messy, or by taking up time?	Very much 	A lot 	A little 	Not at all 	Not relevant 

Please check you have answered EVERY question. Thank you.

15.6 Appendix F – EuroQol-5D-5L

Please check the box that describes your health TODAY.

Mobility

- I have no problems walking
- I have slight problems walking
- I have moderate problems walking
- I have severe problems walking
- I am unable walk
-

Self-Care

- I have no problems washing or dressing myself
- I have slight problems washing or dressing myself
- I have moderate problems washing or dressing myself
- I have severe problems washing or dressing myself
- I am unable to wash or dress myself

Usual Activities

- I have no problems doing my usual activities
- I have slight problems doing my usual activities
- I have moderate problems doing my usual activities
- I have severe problems doing my usual activities
- I am unable to do my usual activities

Pain/Discomfort

- I have no pain or discomfort
- I have slight pain or discomfort
- I have moderate pain or discomfort
- I have severe pain or discomfort
- I am in extreme pain or discomfort

Anxiety/Depression

[figure not shown]
- I am not anxious or depressed
- I am slightly anxious or depressed
- I am moderately anxious or depressed
- I am severely anxious or depressed
- I am extremely anxious or depressed

We would like to know how good or bad your health is TODAY. This scale is numbered from 0 to 100. 100 means the best health you can imagine. 0 means the worse health you can imagine. Please click on the scale to indicate how your health is TODAY.

Visual Analogue Scale (VAS)	

15.7 Appendix G – Visual Analog Scale, Itch

Please rate your itch over the past 24 hours.

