3 BACKGROUND AND SIGNIFICANCE

Palmoplantar pustulosis (PPP) is a limited form of pustular psoriasis characterized by persistent, sterile macroscopic pustules on the palms and/or soles¹ and associated with significant morbidity. PPP is a rare disease with an estimated one-year prevalence between 0.005% - 0.12%.¹⁻³ It has been reported as a solitary disease and in patients with a history of plaque psoriasis.

Previously considered a subtype of psoriasis, important differences identified in the immune dysregulation between psoriasis and PPP suggest they are distinct entities. Genetic susceptibility to plaque psoriasis is polygenic, with 63 genes accounting for 28% of the heritability.⁴ Genes associated with antigen presentation, keratinocyte proliferation and differentiation, and production of pro-inflammatory cytokines in TH-17 cells all play an important role.⁵ A different genetic profile has been associated with pustular psoriasis. Coding mutations in IL36RN, CARD14, AP1S3, SERPINA3, and MPO that affect IL-1 and IL-36 signaling have been associated with the clinical spectrum of pustular psoriasis.⁵ Additionally, the inflammatory profiles between plaque psoriasis and pustular psoriasis have key differences. Plaque psoriasis is a T-cell mediated disease, largely driven by the IL-23/Th-17 pathway.⁶ Overexpression of IL-23 by activated dendritic cells stimulates Th-17 differentiation, cell survival, and proliferation, resulting in the production of additional cytokines: IL-17A, IL-22, and INF- γ . These cytokines cause the activation and hyperproliferation of keratinocytes, resulting in the characteristic plaque development.⁷ In PPP IL-8, IL-36 gamma and IL-36Ra have been found to be overexpressed in lesional skin.⁸ The IL-17A pathway is thought to play a more important role in PPP compared to plaque psoriasis.⁹

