Deucravacitinib has previously demonstrated efficacy in phase II and phase III trials of plaque psoriasis. In the Phase 2 randomized, double-blind, parallel-group, clinical study of increasing doses deucravacitinib placebo in subjects with moderate to severe PsO. The Deucravacitinib treatment demonstrated a dose-dependent improvement in PASI 75, with the 3 highest doses of 3 mg BID, 6 mg BID, and 12 mg QD showing similar responses of 68.9%, 66.7%, and 75.0%, respectively, versus placebo response of 6.7%.²⁰ In the 2 Phase III studies in psoriasis (NCT03624127, NCT03611751), deucravacitinib demonstrated robust and statistically significant efficacy compared with placebo and apremilast, with clinically meaningful improvements in multiple clinical and quality of life parameters in a broad population of patients with moderate-to-severe psoriasis naïve to prior treatment or treatment experienced.²¹ Given that IL-12 and IL-23 are involved in the pathogenesis of both plaque psoriasis and palmoplantar pustulosis, deucravacitinib is an exciting potential novel therapy for an orphan disease and further investigation is warranted.

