6.3 Exclusion Criteria

- Participants with other immune-mediated conditions requiring concurrent systemic immunosuppressant treatments
- Current/recent administration of PPP-specific medications including:
 - Rituximab within 6 months of the baseline visit
 - Biologics (including adalimumab, anakinra, brodalumab, certolizumab, etanercept, golimumab, guselkumab, infliximab, ixekizumab, rizankizumab, secukinumab, spesolimab, tildrakizumab, ustekinumab) within 12 weeks of baseline visit.
 - Systemic steroids, oral immunosuppressants (azathioprine, cyclosporine, methotrexate, mycophenolate mofetil, tacrolimus), oral retinoids (acitretin, isotretinoin), apremilast, or dapsone within 4 weeks of baseline visit
 - Phototherapy within 4 weeks of baseline visit
 - Prescription topical medications (including calcineurin inhibitors, crisaborole, retinoids, steroids, tar, vitamin D analogs) within 2 weeks of baseline visit

- History of active infection and/or febrile illness within 7 days; or infection requiring antibiotic treatment within 30 days; or serious infection requiring hospitalization and/or IV antibiotics within 90 days
- Evidence of other infection including:
 - Active or untreated latent tuberculosis, defined as radiographic or laboratory evidence of active TB or positive quantiferon or PPD, unless the subject has completed the recommended treatment)
 - human immunodeficiency virus infection (positive HIV antibody)
 - Active hepatitis B
 - Active Hepatitis C
- Evidence of clinically significant laboratory abnormality including:
 - Absolute WBC count < 3000/mm³
 - Platelet count < 100,000/mm³
 - Hemoglobin < 9.0 g/dl
 - ALT or AST > 3 times the upper limit of normal
- History of cancer within the past 5 years, excluding treated non-melanoma skin cancer (basal cell carcinoma, squamous cell carcinoma)
- Other uncontrolled chronic medical condition that may interfere with a patient's ability to participate in the clinical trial
- Major surgery within 4 weeks of baseline visit
- Receipt of live vaccine within 8 weeks of baseline visit
- Pregnant or breastfeeding individuals
- Inability to comply with any of the study procedures
- Individuals who are incarcerated or compulsory detained

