- **EuroQol-5D (EQ-5D-5L) (Appendix F):** The EQ-5D is a validated, reliable, and responsive instrument widely used in clinical trials where respondents rate their health in each of 5 dimensions: mobility, self-care, usual activities, pain/discomfort, and anxiety depression.²⁴ This decision results in a 1-digit number that expresses the level selected for that dimension. The digits for the five dimensions can be combined into a 5-digit number that describes the patient's health state. EQ-5D questionnaire also includes a Visual Analog Scale (VAS), by which respondents can report their perceived health status with a grade ranging from 0 (the worst possible health status) to 100 (the best possible health status).
- **Visual Analog Scale, Itch (Appendix G):** The itch visual analogue scale (VAS-itch) is a patient reported pruritis assessment that has been shown to be valid and reliable in the measurement of pruritis and is widely used in dermatology clinical trials.^{25,26} The VAS-itch is a 10 cm line on which patients mark their pruritis intensity on a scale from "no itch" (0 points) to "worst imaginable itch" (10 points).²⁷ The VAS-itch can be interpreted as 0–3 points represents mild pruritis, ≥ 3–7 points moderate pruritis, ≥ 7–9 points severe pruritis, and ≥ 9 points severe pruritis.²⁸
- **Visual Analog Scale, Pain (Appendix H):** The pain visual analogue (VAS-pain) is a patient reported instrument that measures pain intensity. Patients are asked to place a line perpendicular to the VAS line at the point that represents their pain intensity over the past 24 hours. It has been widely used in diverse adult populations, including those with rheumatic diseases.²⁹ The VAS-pain is a continuous 10cm line, anchored by 2 verbal descriptors, one for each symptom extreme. The following cut points on the pain VAS have been recommended to measure postsurgical pain: no pain (0–4 mm), mild pain (5–44 mm), moderate pain (45–74 mm), and severe pain (75– 100 mm).³⁰ In patients with rheumatoid arthritis, the minimal clinically significant change has been estimated as 1.1 points on an 11-point scale (or 11 points on a 100-point scale).³¹

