15.8 Appendix H – Visual Analog Scale, Pain

Please rate your pain over the past 24 hours.

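### The itch and pain VAS items name no body site, so in patients with coexisting plaque psoriasis some change in the patient-reported endpoints could come from outside the palms and soles

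*Combined protocol and SAP*

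**What the plan says.** **Symptom scales.** Appendix G reads "Please rate your itch over the past 24 hours" and Appendix H reads "Please rate your pain over the past 24 hours". Section 8.3 adds no site: for pain the patient marks "the point that represents their pain intensity over the past 24 hours", and the itch anchors run from no itch to the worst imaginable.

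**Quality of life.** The DLQI in Appendix E opens with "The aim of this questionnaire is to measure how much your skin problem has affected your life OVER THE LAST WEEK". The EQ-5D in Appendix F begins "Please check the box that describes your health TODAY". Both are general by design.

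**Investigator scales.** Appendix C scores ppPASI on each palm and each sole. Appendix D confines the PGA to palms and soles.

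**Who may enrol.** Section 3 says of PPP: "It has been reported as a solitary disease and in patients with a history of plaque psoriasis". No criterion excludes plaque psoriasis as such. The nearest, in 6.3, is "Participants with other immune-mediated conditions requiring concurrent systemic immunosuppressant treatments".

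**Known effect in plaque psoriasis.** Section 3 reports efficacy in Phase II and III plaque psoriasis trials, with gains in quality of life in the Phase III studies.

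**Analysis.** Section 11.3 plans descriptive summaries of all secondary endpoints. It states no split by coexisting plaque psoriasis and refers to a statistical analysis plan for detailed methods. Appendix B lists no measure of psoriasis outside the palms and soles.

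**The concern.** A patient with plaques on the elbows or scalp as well as PPP, asked to rate itch with no site given, may count itch from anywhere. If the plaques respond and the palms and soles do not, the rating can still fall. DLQI and EQ-5D VAS can move for the same reason.

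This matters because the protocol's rationale is that PPP is distinct from plaque psoriasis and responds unpredictably to drugs that work well there. A reader will take improvement in itch, pain and quality of life as support for an effect on PPP. With one arm and at most 18 patients, a few people can shift a mean, and no control group would show the same shift.

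The investigator scales are already tied to the palms and soles; the two symptom scales are not.

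**Working it through.** **1. The plan's own figure.** The plan gives no figure for this point. Its one power calculation, in 11.2, concerns ppPASI-50. An exact binomial calculation (8 patients, continue with 3 or more responders; 18 patients, reject with 7 or more) gives power 0.8005 at a 50% response rate, matching the stated 0.8. The exact type I error at 20% is 0.0394, under the stated 0.05. Nothing in the present point changes these numbers.

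**2. Which endpoints are open to the problem.**

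| Endpoint | Site named? | Open to change from elsewhere? |
|---|---|---|
| ppPASI-50 (primary at week 16; week 24), ppPASI change | Each palm and sole | No |
| PGA 0/1 | Palms and soles | No |
| Itch VAS, pain VAS | None | Yes |
| DLQI | The skin in general | Yes |
| EQ-5D VAS | General health | Yes |

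**3. Whether such patients can enter.** The 6.3 criterion removes coexisting disease that needs concurrent systemic immunosuppressants. Plaque psoriasis managed with topicals, or not treated, is not excluded. Stopping systemic drugs or phototherapy used for PPP (4-week washout for phototherapy and the listed oral drugs, 12 weeks for biologics) also ends any benefit to plaques. Topicals used only on plaques may or may not stop, because the criteria are framed around PPP treatment.

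**4. Illustrative size.** Let k of 18 patients have active plaques. Each improves by d points on the 0–10 itch VAS because of them, and PPP itch does not change. Then:

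mean improvement = k × d / 18

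| k | d | Mean improvement |
|---|---|---|
| 2 | 2 | 4/18 = 0.22 |
| 2 | 4 | 8/18 = 0.44 |
| 4 | 3 | 12/18 = 0.67 |
| 6 | 4 | 24/18 = 1.33 |
| 7 | 4 | 28/18 = 1.56 |

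Both k and d are assumptions; the documents supply neither. The table shows how the mean depends on them and is not a forecast. No comparable figure is offered for pain, DLQI or EQ-5D VAS.

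**The case against.** Most of the case on the other side limits the point, and much of it stands.

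- A reader might infer that the items ask about the whole body. They do not: they leave the site open. A patient enrolled for PPP with a ppPASI of at least 12 may well rate the palms and soles. The scale graphics are not visible in the available text, although the anchors described in 8.3 name no site.
- A reader might infer that many participants will have active plaques. Section 3 speaks only of a history of plaque psoriasis, and 6.3 removes some of the more severe coexisting disease.
- A reader might take the plaque trial results as support for a 4-point fall. The Phase II responses in section 3 (66.7% to 75.0% against 6.7% on placebo) are PASI 75 rates in moderate to severe psoriasis, not itch data. Persisting PPP itch would also limit how far a single overall rating could fall.
- It is tempting to set the means above against the 1.1 points in 8.3. That is a minimal change for pain in rheumatoid arthritis, not a yardstick for a group mean of itch.
- A reader might conclude that the trial cannot tell the two sources apart at all. ppPASI and PGA are taken at the same visits, so symptom relief without change on the palms and soles would be visible patient by patient. That is a partial check.
- The direction is not assured. Itch or pain from elsewhere that does not respond would dilute a PPP effect.
- The quality-of-life objective names a population, adults with PPP. It does not require that the change come from palmoplantar lesions.
- Section 11.3 defers detail to a statistical analysis plan, so an unstated split cannot be ruled out.

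One answer remains: no later analysis can restore a site that the patient was never shown.

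**Conclusion.** The point holds as a cheap improvement. The two VAS items name no site, patients with plaque psoriasis not needing concurrent systemic immunosuppressants may enrol, and the protocol says the drug works in that disease. Some change in itch, pain, DLQI and EQ-5D VAS could therefore arise outside the palms and soles, and the stated analysis does not separate it.

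The size is unknown. The illustrated mean itch improvement of 0.44 to 1.56 points (k = 2 to 7, d = 4) rests wholly on assumed values and on no change in PPP itch.

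The documents do not support a stronger reading, namely that these endpoints are invalid, that the bias must favour the drug, or that the trial's conclusion is at risk. Only secondary endpoints are touched; their analysis is descriptive, and an uncontrolled open-label trial could not establish cause from them whatever the wording.

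**What to change.** 1. In Appendices G and H, and in the matching text of 8.3, have the patient rate the itch (or pain) of the palms and soles, keeping the 24-hour recall. Settle this before data collection, since change from baseline needs the same item at every visit.
2. At the baseline physical examination already in Appendix B, record whether active plaque psoriasis is present outside the palms and soles (yes/no).
3. In 11.3, add a descriptive summary of change in itch VAS, pain VAS, DLQI and EQ-5D VAS in patients without it. A ppPASI-50 subset is not needed, because that score is already confined to the palms and soles.
4. Leave the DLQI and EQ-5D wording unchanged. The VAS rewording does nothing for those two instruments; only items 2 and 3 help there.

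The cost is a few words in two appendices and 8.3, one yes/no field and one table. The downsides are slightly less comparability with studies that used the unanchored VAS, and a subset too small for more than description.
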